3.2.1.3 Endogenous BPI and LPS Levels Following Hematopoietic Stem Cell Transplant

Levy, [name] and colleagues, and XOMA are presently conducting a study to investigate the endogenous background levels of BPI and LPS in patients undergoing HSCT. Recent human data have shown that, post-conditioning, patient blood levels of endogenous BPI drop to undetectable levels rapidly as the ANC falls. During this period there is a concomitant rise in LBP (indicating endotoxemia); furthermore, as neutrophils recover in these patients, circulating levels of BPI rise and LBP diminish to normal pre-inflammatory levels (Levy, [name], et al., unpublished observations, Figure 2).

Figure 2
Plasma Concentrations in Patients Undergoing HSCT

Based on all of the above, it is hypothesized that continuous administration of opebacan therapy to provide continuous drug levels, before infusion of donor cells, will make BPI available to neutralize circulating endotoxin and ameliorate endotoxin-mediated activation of the innate immune system, thus preventing or reducing complications associated with endotoxemia, including aGvHD.

3.2.1.4 Nonclinical Safety Assessment Summary

The general toxicity of opebacan was assessed in the rat and the monkey using the IV route of administration (bolus administration, continuous and intermittent infusion) for up to 28 days. Doses evaluated in these studies ranged from 2 to 200 mg/kg/day in the rat and from 10 to 200 mg/kg/day in the monkey.

[figure not shown]
Dose-related myocardial toxicity was observed in a single rat and a single monkey study following continuous infusion of formulated opebacan at ≥ 100 mg/kg/day for 3 to 5 days. No cardiotoxicity was seen in a number of other studies where formulated opebacan was continuously administered at doses up to 120 mg/kg/day in the rat and up to 75 mg/kg/day in the monkey for the same or longer duration, and where formulated opebacan was administered intermittently 4 times a day for 28 days at doses up to 150 mg/kg/day in the rat and up to 100 mg/kg/day in the monkey. The later data suggests that the duration of exposure may pose a greater risk of cardiac toxicity than the total daily dose.

Steady-state plasma opebacan levels were calculated for the rat and monkey studies where cardiotoxicity was evident. In the rat study, the steady-state plasma opebacan level corresponding to the cardiotoxic dose was approximately 3 µg/mL, and the no-observed-

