 for all fluids and nutritional sources, intake and output [I&O], and total days of
 parenteral nutrition [TPN]). Assessments requiring daily totals should be
 measured by calendar day (i.e., from midnight to midnight) unless otherwise
 specified by institutional standard practice.
- Vital signs including pulse, blood pressure (systolic/diastolic), respiratory rate, and temperature taken in the morning (i.e., the first waking set of vital signs). If a subject experiences an SAE, vital signs must be taken more frequently, per standard institutional practice.
- Fever (T_{max})
- LPS and LBP
- Soluble markers that may include, but may not be limited to, sCD14, TNF-RI, IL-1, IL-6, IL-8, IL-10, IL-12, and CRP
- Surface markers at select sites only; may include, but may not be limited to, TLR4 and mCD14
- Oral mucositis score (see Appendix 5)
- Continuation of opebacan dosing. Subjects whose conditioning regimen includes TBI will have their opebacan infusion interrupted for 1-hour TBI treatments twice on Day 0 prior to the HSCT procedure. The HSCT will take place after the opebacan infusion has been restarted for at least 2 hours.

Day 1 (Dose Group 5)

Adverse events

- Concomitant medications
- PK sample. Note: PK sample must be drawn from a different vein than that used for opebacan administration.
- Metabolic assessment (Intake and output [I&O] and total days of parenteral nutrition [TPN] only). Assessments requiring daily totals should be measured by calendar day (i.e., from midnight to midnight) unless otherwise specified by institutional standard practice.
- Vital signs including pulse, blood pressure (systolic/diastolic), respiratory rate, and temperature taken in the morning (i.e., the first waking set of vital signs). If a subject experiences an SAE, vital signs must be taken more frequently, per standard institutional practice.
- Fever (T_{max})
- Oral mucositis score (see Appendix 5)
- Cardiac serology (CPK-MB, troponin T, and troponin I)
- Continuation of opebacan dosing

Day 2 (Dose Group 5)

- Adverse events
- Concomitant medications
- Metabolic assessment (Intake and output [I&O] and total days of parenteral nutrition [TPN] only). Assessments requiring daily totals should be measured by calendar day (i.e., from midnight to midnight) unless otherwise specified by institutional standard practice.

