- Oral mucositis score (see Appendix 5)
- LVEF by ECHO or MUGA
- Grading for aGVHD (see Appendix 4)
- Performance score (Karnofsky criteria; see Appendix 3)
- Continuation of opebacan dosing

Day 8 (Dose Group 5)

- Adverse events
- Concomitant medications
- Laboratory evaluations (predose)
 - Chemistries: Sodium, potassium, chloride, bicarbonate, glucose, BUN, creatinine, calcium, phosphorus, magnesium, bilirubin (total, and direct if bilirubin > 2.0 mg/dL), albumin, ALT, AST, LDH, alkaline phosphatase, and total protein
 - Coagulation: PT, PTT, fibringen, and D-Dimers (or FDP or FSP)
 - Urinalysis: Chemistry and microscopic examination
- Metabolic assessment (Intake and output [I&O] and total days of parenteral nutrition [TPN] only). Assessments requiring daily totals should be measured by calendar day (i.e., from midnight to midnight) unless otherwise specified by institutional standard practice.

• Vital signs including pulse, blood pressure (systolic/diastolic), respiratory rate, and temperature taken in the morning (i.e., the first waking set of vital signs). If a subject experiences an SAE, vital signs must be taken more frequently, per standard institutional practice.

- Fever (T_{max})
- LPS and LBP
- Oral mucositis score recorded daily until condition resolves to grade 0 (see Appendix 5)
- Cardiac serology (CPK-MB, cardiac troponin T, and troponin I)
- Continuation of opebacan dosing

Day 9 (Dose Group 5)

- Adverse events
- Concomitant medications
- Metabolic assessment (Intake and output [I&O] and total days of parenteral nutrition [TPN] only). Assessments requiring daily totals should be measured by calendar day (i.e., from midnight to midnight) unless otherwise specified by institutional standard practice.
- Vital signs including pulse, blood pressure (systolic/diastolic), respiratory rate, and temperature taken in the morning (i.e., the first waking set of vital signs). If a subject experiences an SAE, vital signs must be taken more frequently, per standard institutional practice.
- Fever (T_{max})
- Oral mucositis score recorded daily until condition resolves to grade 0 (see Appendix 5)
- Continuation of opebacan dosing

Day 10 (Dose Group 5)

- Adverse events
- Concomitant medications
- PK sample. Note: PK sample must be drawn from a different vein than that used for opebacan administration.
- Laboratory evaluations:
 - Hematology: CBC with differential and platelet count

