6.2 Determination of Sample Size

The sample size for this study is based primarily on PK/PD considerations. The planned accrual is six subjects in each of the five successive dose groups. Formal sample size calculations were not done but past experience with this type of study suggests that this number of subjects will be adequate to characterize the PK/PD profile at each dose level.

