Appendix 1 (continued) Footnotes to Study BPSC030 Schedule of Assessments

- Chemistries include sodium, potassium, chloride, bicarbonate, glucose, BUN, creatinine, calcium, phosphorus, magnesium, bilirubin (total, and direct if bilirubin > 2.0 mg/dL), albumin, ALT, AST, LDH, alkaline phosphatase, CPK with MB fraction (not done if a cardiac serology assessment is done), and total protein. Coagulation includes PT, PTT, fibrinogen, D-Dimers (or FDP or FSP). Urinalysis includes chemistry and microscopic.
- Successful engraftment must be confirmed by three consecutive daily measurements of ANC $\geq 500/\mu L$, with the first of the 3 days occurring no later than Day 28.
- The metabolic assessment includes the following: 1) Caloric source documentation, including volume and type for all fluids and nutritional sources, performed on Days –1, 0, 3, 7, 10, 14, 17, 21, 24, 28, 35, 42, and 49 or until the subject is released from the hospital, whichever occurs first; and 2) Intake and output (I&O) and total days of parenteral nutrition (TPN), performed daily from Day –1 through Day 49 or until the subject is released from the hospital, whichever occurs first. At final screening, the subject or legal guardian will be asked to provide the subject's recent dietary history. Metabolic assessments requiring daily totals should be measured by calendar day (i.e., from midnight to midnight) unless otherwise specified by institutional standard practice.
- Vital signs include pulse, blood pressure (systolic/diastolic), respiratory rate, and temperature taken in the morning (i.e., the first waking set of vital signs). On Day -1 only, body weight must be measured predose to calculate the study drug dose and temperature is measured twice: predose (within one hour prior to the start of infusion) and postdose (within four hours after the start of infusion). If a subject experiences an SAE, vital signs must be taken more frequently, per standard institutional practice. Vital signs must be recorded every day from Day -1 through Day 49 or until the subject is released from the hospital, whichever occurs first.
- T_{max} is the highest temperature recorded of all measurements taken during a calendar day (i.e., midnight to midnight). On Day –1 only, T_{max} is measured for two separate periods: predose (within one hour prior to the start of infusion) and postdose (within four hours after the start of infusion).
- ¹⁷ On Day –3, LPS but not LBP will be assessed.

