Appendix 2: Study BPSC030 PK Sampling Schedule¹

Study Day	sscreen			-1			0	1			2			3			6			7	10			13			14	100
Minutes ²	Pre	Pre	30	45	90	270	1440	2880	EOI	15	30	60	240	1440	EOI	15	30	60	240	1440		EOI	15	30	60	240	1440	
Group 1	X^3	X^3	X	X	X	X	X	X	X	X	X	X	X	X														X
Group 2	X^3	X^3	X	X	X	X	X	X	X	X	X	X	X	X														X
Group 3	X^3	X^3	X	X	X	X	X	X	X	X	X	X	X	X														X
Group 4	X^3	X^3	X	X	X	X	X	X							X	X	X	X	X	X								X
Group 5	X^3	X^3	X	X	X	X	X	X							X^4						X	X	X	X	X	X	X	X
Donor	X^3																											

¹ PK sample must be drawn from a different vein than that used for opebacan administration.

For Days –1, 0, and 1, sampling time is shown in minutes following initiation of opebacan treatment. For Days 2 and 3 (Groups 1, 2, and 3), Days 6 and 7 (Group 4), and Days 13 and 14 (Group 5), sampling times are shown in minutes following the end of infusion (EOI). The "EOI" sample must be drawn within one hour prior to the end of the opebacan infusion. The acceptable windows for the other PK draws are as follows: 15 ± 5 minutes, 30 ± 5 minutes, 45 ± 5 minutes, 60 ± 10 minutes, 90 ± 15 minutes, 240 ± 30 minutes, 270 ± 30 minutes, 1440 ± 60 minutes, and 2880 ± 60 minutes.

³ The PK samples for the donor and subject at prescreen and for the subject at predose on Day –1 are used for measuring the level of endogenous BPI.

The PK sample for Group 5 subjects on Day 6 is drawn along with other blood draws on that day. Though it appears in the EOI column, the infusion for this dose group does not end until Day 13.

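### Group 5 has no scheduled cardiac marker or LVEF in the last 5 of its 14 infusion days, because the cardiac calendar was not adapted to the longer infusion

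*Supplement*

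**What the plan says.** Section 4.3.2.3 and Appendix 1 agree on the Group 5 calendar. Cardiac serology ("Cardiac serology (CPK-MB, cardiac troponin T, and troponin I") is due at prescreen, on Day -1 before dosing, and on Days 1, 4, 8, 14, 21 and 28, then on Days 35, 42 and 49 for subjects still in hospital. "LVEF by ECHO or MUGA" is due at prescreen and on Days -1, 7, 14, 21, 28 and 100. ECG is done at prescreen only. The Day 9 to Day 13 lists contain no cardiac item. Appendix 2 notes for Group 5 that "the infusion for this dose group does not end until Day 13".

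The chemistry panel does not fill the interval. Its CPK component is "CPK with MB fraction (not done if a cardiac serology assessment is done"), and Group 5 has no chemistries between Day 8 and Day 14.

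On why the heart is watched, section 3.2.1.4 reports dose-related myocardial toxicity in one rat and one monkey study and concludes: "The later data suggests that the duration of exposure may pose a greater risk of cardiac toxicity than the total daily dose". Two steps of the design, Group 3 to 4 and Group 4 to 5, hold the daily rate at 12 mg/kg and lengthen the infusion, from 3 to 7 and then to 14 days.

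**The concern.** Appendix 1 gives the 3-day, 7-day and 14-day cohorts separate rows for PK, for chemistry, coagulation and urinalysis, and for CBC, so those calendars follow infusion length. The cardiac serology and LVEF rows are common to all groups. The longest time on drug without a cardiac test therefore falls in the group that exists to test long infusion, and myocardial toxicity is the nonclinical finding from which section 3.2.1.4 derives its ceiling on plasma concentration.

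The highest prior human regimen described in that section was 6 mg/kg/day for 3 days, so there is little earlier clinical information on the late part of a 14-day infusion at twice that rate. Sections 3.3.2 and 4.5.1 have a subject with a confirmed DLT discontinue study drug. A silent change first seen on Day 14 comes after dosing has ended. At stake is how well the Group 5 data describe cardiac safety during days 10 to 14 of continuous exposure.

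**Working it through.** No power or sample-size figure bears on this point. Section 6.2 states: "Formal sample size calculations were not done but past experience with this type of study suggests" that six per group is enough.

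**The plan's own figure.** Table 1 gives Group 5 a total of 172 mg/kg. Check: 4 + 12 × 14 = 172. The other groups also reproduce: 4 + 6 × 3 = 22; 4 + 9 × 3 = 31; 4 + 12 × 3 = 40; 4 + 12 × 7 = 88.

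**Inputs.** Infusion starts on Day -1 in all groups and ends on Day 2 (Groups 1-3), Day 6 (Group 4) or Day 13 (Group 5). Serology days are -1 (predose), 1, 4, 8 and 14.

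**Time on drug after the last serology sample** (end-of-infusion day minus last serology day before it):

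| Group | Last sample on drug | End of infusion | Days uncovered | Share of infusion | Dose in that stretch |
|---|---|---|---|---|---|
| 1-3 | Day 1 | Day 2 | 1 | 1/3 = 33% | 6, 9 or 12 mg/kg |
| 4 | Day 4 | Day 6 | 2 | 2/7 = 29% | 2 × 12 = 24 mg/kg |
| 5 | Day 8 | Day 13 | 5 | 5/14 = 36% | 5 × 12 = 60 mg/kg |

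For Group 5, dose to Day 8 is 4 + 12 × 9 = 112 mg/kg, and 172 - 112 = 60 mg/kg, or 60/172 = 35% of the total. As a share of the infusion the three rows are similar. The difference is in days on drug and in dose: the Group 5 stretch is longer than the whole 3-day infusion of Groups 1-3, and its 60 mg/kg exceeds the full Group 3 dose of 40 mg/kg.

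**Interval between Group 5 samples.** Day -1 to 1 is 2 days, 1 to 4 is 3, 4 to 8 is 4, and 8 to 14 is 6. The Day 14 sample falls 14 - 13 = 1 day after the infusion ends. The longest interval comes at the end of the longest exposure.

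**LVEF.** The two scans around this period are Days 7 and 14, so Days 8 to 13 have none.

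**Precision.** These are whole calendar days. The protocol fixes no clock time for the Day 8 sample or for the end of infusion on Day 13, so an individual subject's uncovered stretch could be anywhere from just over 4 to just under 6 days.

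**The case against.** The strongest reply is that this is delayed detection and not lost information. Full serology and LVEF are done on Day 14 and again on Days 21 and 28, and vital signs and adverse events are recorded on each of Days 9 to 13. The protocol also addresses the 14-day regimen directly. It cites a rat NOAEL of 50 mg/kg/day over 14 days (about 1 µg/mL) and a monkey NOAEL of 75 mg/kg/day over 28 days (about 10 µg/mL), against about 0.5 µg/mL expected here. The animal toxicity arose at 100 mg/kg/day or more. Those points stand and limit the size of the concern. They support giving the regimen, but they do not replace measurements taken during it.

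A second reply is that Group 5 has the best coverage just after dosing, with troponin and LVEF one day after the end of infusion. In Groups 1-3 the delays are 2 and 5 days, and in Group 4 they are 2 days and 1 day. That is correct for troponin, and for LVEF against Groups 1-3. It is not so for CPK-MB, which Groups 1-4 also have one day after infusion through the chemistry panel (Day 3 or Day 7). In any case it does not shorten the stretch on drug.

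A reader might infer four stronger things that the documents do not support:

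- **That the protocol says duration drives cardiotoxicity.** Its wording is a hedged inference from animal data.
- **That the whole second week of infusion is unmonitored.** That week starts on about Day 6, so Day 7 LVEF and Day 8 serology fall inside it.
- **That a late rise would be missed altogether.** Only one that starts after Day 8 and clears before Day 14 would escape, and the documents give no marker kinetics from which to judge how likely that is.
- **That the DLT count is weakened.** This is not shown. The DLT window runs to 4 weeks from administration, DSMB review follows Day 28, and section 5.3 says an isolated laboratory abnormality may not count as an adverse event. Group 5 is also the last group, so no escalation waits on it.

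**Conclusion.** The gap is real and modest. In Group 5 the last 5 of 14 infusion days (36%, about 60 of 172 mg/kg) have no scheduled cardiac marker or LVEF, against a 1-day stretch without serology in Groups 1-3 and 2 days in Group 4. The calendar was carried over unchanged while other laboratory rows were adapted, and section 3.2.1.4 gives a reason to adapt this one.

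The practical effect is that scheduled testing would first show a change starting after Day 8 about a day after dosing ends, and could miss a transient one. A persistent change would be found on Day 14. This rests on the calendar-day count above and on scheduled tests only; an investigator may order others. Appendix 1 and section 4.3.2.3 do not contradict each other, so this is a cheap improvement to the safety data and not the repair of an error.

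**What to change.** Reconcile the Group 5 cardiac schedule with section 3.2.1.4. In section 4.3.2.3 and Appendix 1, add the existing panel (CPK-MB, troponin T, troponin I) to blood already drawn on Day 10. This splits the 6-day interval into 2 and 4 days and cuts the uncovered end of the infusion from 5 to 3 days (3/14 = 21%).

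If a true end-of-infusion value is wanted, attach a second panel to the Day 13 PK sample taken within the hour before the infusion stops. It should not go with the Day 13 CBC: assessments that day are by default done after the infusion ends, so that sample would nearly duplicate Day 14. Include the added values in the Group 5 laboratory summary under section 6.5.2.

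The cost for six subjects is 6 panels (6 × 3 = 18 analyte results) for Day 10 alone, or 12 panels (36 results) with Day 13. These figures double if the cohort expands to 12. Blood volume rises slightly. Section 4.3 does not list cardiac serology among the locally run tests and sends other samples to a central laboratory, so the assured gain is better safety data and not real-time action. How results are acted on stays with the investigators and the DSMB.

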4.4 Donor Assessments

Before any evaluations or measurements are performed on the donor, the donor or legal guardian must be fully informed and sign a XOMA/IRB-approved informed consent form for participation in this study. If a donor declines to consent to study participation, the subject who receives that donor's stem cells will continue to be included in the study. The following assessments must be performed and samples collected on donors prior to harvest of donor cells:

- Signed XOMA/IRB-approved informed consent
- Demographic information (sex, age, race/ethnicity)

- Medical history, including virology and serology status
- DNA testing (SNPs for markers such as TLR and TNF) at select sites only
- PK sample for measuring level of endogenous BPI. Note: PK sample must be drawn from a different vein than that used for opebacan administration.
- LPS and LBP
- LPS-induced TNF and IL-6 at select sites only
- Anti-opebacan antibody response

4.5 Discontinuation

4.5.1 Subject Discontinuation

Subjects may withdraw or be withdrawn from the study at any time. Every effort should be made to obtain complete follow-up information on subjects who receive any amount of opebacan and discontinue from the study prematurely. The reason(s) for a subject's discontinuation from the study must be clearly documented in the subject's medical records and on the CRF

A subject who experiences DLT at any dose level will discontinue study drug. After receiving treatment for the toxicity (if necessary), the subject will be closely monitored until the toxicity is resolved to no worse than grade 2 (grade 1 if reported toxicity is initially grade 2) severity or is stabilized, at which point he/she will be removed from the study.

In the event that a subject discontinues participation in the study prior to receiving opebacan, the subject will be replaced. No follow-up or additional procedures will be performed on subjects discontinuing prior to receiving opebacan.

Subjects will also be replaced if they do not receive at least 80% of their scheduled dose of opebacan and/or do not complete assessments for at least 7 days following the end of their opebacan infusion.

If the subject discontinues participation in the study after receiving any amount of opebacan, every effort should be made to complete as many subsequent protocol evaluations as possible.

4.5.2 Study Discontinuation

XOMA has the right to terminate this study at any time for any reason. Reasons for terminating the study may include the following:

- The incidence or severity of AEs indicates a potential health hazard to subjects.
- Subject enrollment is unsatisfactory.

5.0 ASSESSMENT OF SAFETY

All regulations stated in 21 CFR Parts 50, 56 and 312 and recommendations outlined in the ICH Guidelines for Good Clinical Practice will be adhered to throughout this trial. The safety of the drug will be assessed by multiple subject assessments of vital signs, physical exams, clinical tests and laboratory evaluations. Concomitant medications and adverse events will be monitored and tracked.

Following a comprehensive baseline evaluation of each subject, subject safety will be monitored by evaluating all adverse events (AEs) that occur following treatment with study drug and by performing periodic physical examinations and laboratory tests (hematology, chemistry, and urinalysis).

Once any evidence of unexpected clinical and/or laboratory toxicity is noticed, the Investigator should take appropriate and prompt remedial measures while trying to elucidate the etiology of the condition. The subjects will be followed until the condition resolves or becomes chronic or stable. The Investigator should document and report the event to the Sponsor.

Safety will be monitored and tracked for every subject given any amount of study drug.

5.1 Adverse Events

The occurrence of an adverse event will be determined based on observed or volunteered signs and symptoms, as well as changes in the subject's physical examination and laboratory results.

Adverse events that occur during the study will be recorded on the appropriate AE pages of the CRF. On Day -1, a "signs and symptoms inventory" CRF page will be completed prior to initial dosing with opebacan.

An AE is defined as any untoward medical occurrence (e.g., sign, symptom, disease, syndrome, intercurrent illness, abnormal laboratory finding) that emerges or worsens relative to pretreatment baseline during the study, regardless of the suspected cause. Untoward medical events that occur from the time the subject signs the informed consent form to the time the administration of the drug starts are not considered adverse events, and should be recorded under medical history.

Acute infusional adverse events may include headache, fever, chills, myalgia or nausea experienced 12 to 48 hours following initiation of IV administration of study drug.

All AEs will be evaluated by the Investigator for their seriousness, severity, relationship to study drug, and outcome.

An AE occurring at any dose (including overdose) should be classified as **SERIOUS** if:

- It resulted in death (i.e., the AE caused or led to death).
- It was life threatening (i.e., the AE placed the subject at immediate risk of death; an AE should not be classified as life-threatening if it hypothetically might have caused death if it were more severe).
- It required or prolonged inpatient hospitalization (i.e., the AE required at least a 24-hour inpatient hospitalization or prolonged a hospitalization beyond the expected length of stay; hospitalizations for elective medical/surgical procedures, scheduled treatments, or routine check-ups are not SAEs by this criterion).
- It was disabling (i.e., the AE resulted in a substantial disruption of the subject's ability to carry out normal life functions).
- It resulted in a congenital anomaly/birth defect (i.e., an adverse outcome in a child or fetus of a subject exposed to the molecule or study drug prior to conception or during pregnancy).
- It does not meet any of the above criteria for a serious AE but may jeopardize the subject or may require medical or surgical intervention to prevent one of the outcomes listed above

Note: As stated in Section 5.2, certain transplant-related experiences will not be reported as serious adverse events unless the event is life threatening or fatal.

All adverse events will be graded for severity according to the NCI Common Terminology Criteria for Adverse Events (CTCAE), version 3.0 (available on line at http://ctep.cancer.gov/reporting/ctc.html).

Using the following criteria, Investigators also need to assess whether there is a reasonable possibility that study drug caused or contributed to the AE:

Yes (possibly, probably, or definitely related):

• There is a clinically plausible time sequence between onset of the AE and study drug administration

AND/OR

• There is a biologically plausible mechanism for study drug causing or contributing to the AE

No (unlikely, unrelated):

- Another cause of the AE is most plausible AND/OR
- A clinically plausible temporal sequence is inconsistent with the onset of the AE and study drug administration

AND/OR

• A causal relationship is considered biologically implausible

The Principal Investigator will be asked to list any other suspected causes.

